1. Abstract

Both Sleeve Gastrectomy (SG) and Roux-en-Y Gastric Bypass (RYGB) increase GLP-1 concentrations, although this is of lesser magnitude in SG compared to RYGB. We have data to suggest that endogenous GLP-1 is at least partially responsible for reducing free-choice caloric intake after RYGB, providing a mechanism underlying differences between procedures. Inhibition of GLP-1 action with Exendin-9,39 after RYGB accelerates gastric emptying. These observations suggest that factors other than anatomy regulate the upper gastrointestinal response to food ingestion. It is therefore reasonable to consider that the postprandial rise in GLP-1 might affect feeding behavior after RYGB, and to a lesser extent SG, where the increase in GLP-1 is less marked.

Title:	Exendin (9,39) and Satiety After Bariatric Surgery
Funding Source/Grant No.:	Obesity Society
IRB Number:	
IRB Approval Date:	
Principal Investigator:	[name] MD
Co-investigator(s):	[name] MD; [name] MD

I. Hypothesis and Specific Aims

The *overall aim* of this application is to determine the contribution of the elevated incretin hormone concentrations seen after certain types of bariatric surgery to the regulation of food intake and satiety. Roux-en-Y Gastric Bypass (RYGB) and sleeve gastrectomy (SG) are the commonest forms of bariatric surgery and raise Glucagon-like Peptide-1 (GLP-1) secretion although to markedly different degrees. Recently, we demonstrated that inhibition of GLP-1 actions by Exendin-9,39 accelerates gastrointestinal transit implying a role of GLP-1 in gastrointestinal function after gastric bypass (1). Given that GLP-1 affects upper gastrointestinal function, it seems reasonable to postulate that GLP-1 may play a role in food intake after gastric bypass (2; 3). In support of this we have generated preliminary data to show that Exendin-9,39 increases oral intake after bariatric surgery.

Specific Aim: Determine the effects of GLP-1 Receptor blockade on caloric intake and gastrointestinal transit in subjects after SG and after RYGB.

1° Hypothesis: Blockade of the GLP-1 receptor in subjects after RYGB produces equivalent caloric intake to that observed after SG.

2° Hypothesis: Blockade of the GLP-1 receptor accelerates gastrointestinal transit in subjects after RYGB but not after SG.

[figure not shown]
II. Background and Significance

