
1) Power Calculation: In a prior experiment we observed an overall mean value \pm (SD) of Gastric Emptying = $145 \pm (27)$ min(60) and $745 \pm (86)$ Cal(44). Assuming similar variation, 25 subjects per group would provide approximately 85% power (at a 2-sided 0.05 α level), to detect a 15% change in GE₅₀ (time taken to empty 50% of gastric contents) and a 10% change in caloric intake in each group in response to Exendin-9,39.

1) Statistical Analysis: Data will be presented as (observed) mean \pm SEM. The initial analyses will compare the within-group effect of treatment (Exendin-9,39) with the data observed in the study where saline is infused. This analysis will use a paired t-test, or signed-rank test, as warranted. An ANCOVA model incorporating the corresponding baseline study value as a covariate (e.g. GE₅₀) will be used to test differences in the response to Exendin-9,39 between groups (RYGB vs. SG). The ANCOVA model will also include age, gender and weight as covariates. A p -value < 0.05 will be considered to be statistically significant.

1) Interpretation: We will test the hypothesis that blockade of the GLP-1 receptor (GLP1R) in subjects after RYGB increases caloric intake to amounts that do not differ from those consumed after SG in the presence or absence of Exendin-9,39 infusion. We anticipate that after RYGB, subjects presented with a free choice buffet will eat less than subjects after SG during saline infusion. However, Exendin-9,39 increases caloric intake during a free choice buffet after RYGB. This supports the suggestion that the high concentrations of GLP-1 observed after RYGB alters feeding behavior, decreasing caloric intake. Given the lower concentrations of GLP-1 observed after eating in SG, we anticipate that Exendin-9,39 will have little effects, if any, on caloric intake in subjects post-SG.

To test our secondary hypothesis, we will measure gastrointestinal transit using a labelled meal as outlined above during the two studies. We anticipate that in subjects after RYGB, inhibition of endogenous GLP-1 by Exendin-9,39 will accelerate gastrointestinal implying that the high concentrations of GLP-1 observed after RYGB delay gastrointestinal transit. Conversely, in the absence of very significant elevations in endogenous GLP-1 after SG, we expect little effect of Exendin-9,39 on gastrointestinal transit – as observed previously in subjects with an intact upper gastrointestinal tract (1).

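### The primary hypothesis says that intake after RYGB under blockade is equivalent to intake after SG, but no planned analysis estimates that contrast and no margin or confidence-interval rule is set

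*Combined protocol and SAP*

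**What the plan says.** Section I (Hypothesis and Specific Aims) gives the primary hypothesis: "Blockade of the GLP-1 receptor in subjects after RYGB produces equivalent caloric intake to that observed after SG". It does not say which SG study day is meant. The Interpretation paragraph of section IV says the hypothesis will be tested and names both days: intake after RYGB "increases caloric intake to amounts that do not differ from those consumed after SG in the presence or absence of Exendin-9,39 infusion". The same paragraph states the expected starting position: "We anticipate that after RYGB, subjects presented with a free choice buffet will eat less than subjects after SG during saline infusion". No size is given for that gap.

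The Statistical Analysis paragraph lists two analyses. First: "The initial analyses will compare the within-group effect of treatment (Exendin-9,39) with the data observed in the study where saline is infused", by paired t-test or signed-rank test. Second: "An ANCOVA model incorporating the corresponding baseline study value as a covariate", together with age, gender and weight, to compare the two surgical groups on their response to blockade. The only criterion is p < 0.05. On presentation it says "Data will be presented as (observed) mean" with SEM.

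The Power Calculation claims about 85% power with 25 per group for a "10% change in caloric intake in each group in response to Exendin-9,39". No equivalence margin or CI rule appears anywhere in the document.

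**The concern.** Equivalence between RYGB on the Exendin-9,39 day and SG is a between-group comparison of mean intake. The Interpretation wording implies two such contrasts:

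- A: RYGB/Exendin minus SG/saline
- B: RYGB/Exendin minus SG/Exendin

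Neither is listed. The paired test asks whether RYGB intake rose. The ANCOVA asks whether it rose more than SG intake did. Neither asks whether it reached the SG level. With no margin, no result is defined in advance as confirming or refuting the hypothesis, so any statement of equivalence would rest on a criterion chosen after the data are seen and would have no controlled error rate. The item affected is the one labelled primary.

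**Working it through.** **Inputs from the plan.** Mean intake 745 and SD 86 (Power Calculation; the plan's Cal, written kcal here), 25 per group, two-sided alpha 0.05. The expected saline-day gap has a direction but no size. Within-person correlation, gap sizes and margins are not given, so those below are assumptions.

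**1. The plan's own power figure.** A 10% change is 74.5 kcal. The two-sample standard error is 86 × √(2/25) = 24.3, so the noncentrality is 74.5/24.3 = 3.06. Two-sided t power on 48 df is 85.1%, which matches the stated 85%. The plan attaches this figure to a within-group change. It is power to detect a difference, not to show equivalence.

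**2. What the ANCOVA estimates.** The protocol describes no buffet measurement other than the one on each study day, so for intake the baseline study value is read here as the saline-day value. The group term is then

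(Exendin-day difference) − slope × (saline-day difference),

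whether the outcome is entered as the Exendin-day value or as the change. It equals contrast B only if the slope is zero or the groups match on the saline day, and the plan expects them not to match. It never gives contrast A. The age, gender and weight covariates are left out below for simplicity.

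Illustration: assumed saline-day gap of 74.5 kcal (RYGB lower), no effect in SG, equal SDs on both days (so slope = correlation r), r = 0.3/0.5/0.7.

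- Gap fully closed (hypothesis true): 0 − r × (−74.5) = +22/+37/+52 kcal.
- Half the gap remaining: −37.25 + r × 74.5 = −15/0/+15 kcal.

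So the group term is not zero when the hypothesis is true, and it can be zero when the hypothesis is false.

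**3. What the paired test shows.** At an assumed gap of 149 kcal and the same correlations, the RYGB paired test is significant with probability 94–100% whether the gap closes fully or only by half. At 74.5 kcal it is significant with probability 94–100% (closed) against 42–77% (half closed). How well it separates the two cases depends on a gap that the plan does not state.

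**4. What the level contrast could deliver.** For one unadjusted contrast, the 90% CI half-width is 1.677 × 24.3 = 40.8 kcal. The table gives the probability that the 90% CI lies inside the margin when the true difference is zero (SDs of 100 and 120 are assumed):

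| Margin (kcal) | SD 86 | SD 100 | SD 120 |
|---|---|---|---|
| ±74.5 | 83% | 66% | 40% |
| ±60 | 57% | 35% | 10% |
| ±50 | 30% | 10% | 1% |

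The smallest margin with 80% power is ±72, ±84 and ±101 kcal at these SDs. Requiring both contrasts at SD 86, over the same range of r, gives 73–76%, 38–44% and 12–16% at ±74.5, ±60 and ±50.

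**5. With the plan's covariates.** If age, gender and weight explain 0/10/20/30% of the variance in group membership (assumed) and leave the residual SD at 86, power for one contrast at ±74.5 is 83%/78%/71%/62% (45 df, variance inflated by 1/(1 − R²)). Any reduction in residual SD would offset this.

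**The case against.** This is a small mechanistic study, which the Summary / Future Directions paragraph presents as groundwork for a later randomised trial. The planned tests fit the Specific Aim: the effect of blockade in each group and the difference in response. A positive ANCOVA term is what the plan anticipates. Reporting means with SEM could also let a reader form the level contrasts: each expected SEM is 86/√25 = 17.2, so the standard error of a contrast is √(17.2² + 17.2²) = 24.3. All of this stands. It shows that the analyses are useful, not that they test the stated primary hypothesis, and summary statistics supply no margin or decision rule.

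Two stronger readings should be resisted. A reader might infer that the trial will declare equivalence falsely at a known rate. If a non-significant two-sample t-test were taken as equivalence, a true 37 kcal difference (5% of 745) would pass 68% of the time and a 74.5 kcal difference 15% of the time. The plan states no such rule, so these are not its error rates. A reader might also infer that the ANCOVA is wrong. The plan uses it only to compare responses and never says that a zero coefficient means equivalence. Step 2 shows only that it cannot stand in for the missing contrast.

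The figures 745 and 86 also need caution. The plan cites them from a study whose title describes DPP-4 inhibition and satiation in type 2 diabetes, whereas this trial measures buffet intake after bariatric surgery and excludes diabetes.

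**Conclusion.** The concern holds as a mismatch between hypothesis and analysis. The document says it will test equivalence of intake levels, but it plans no analysis that estimates either level contrast, powers only a within-group change, and sets no margin or CI rule. It therefore cannot support a conclusion of equivalence. This part rests on the text alone and needs no assumed numbers, apart from the reading of the baseline value in the ANCOVA argument.

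The figures show what an equivalence claim would cost: about 83% power at ±74.5 kcal and 30% at ±50 kcal for one unadjusted contrast. They depend on the plan's SD of 86, which may not carry over, and on margins that are illustrations only. The documents do not support saying that 25 per group is too few, because that depends on a margin nobody has yet justified.

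**What to change.** Revise section IV by one of two routes.

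**(a) Keep equivalence.**

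- Add RYGB/Exendin minus SG/saline and RYGB/Exendin minus SG/Exendin on data already planned. Name one as primary or require both, and align the section I wording with that choice.
- Keep age, gender and weight as covariates, because the surgical groups are not randomised. Leave out saline-day intake, for the reason in step 2. Show the unadjusted contrast as a sensitivity analysis.
- Report estimates with CIs. Claim equivalence only if the 90% CI lies within a margin that the sponsor justifies before data are seen; otherwise report that equivalence was not shown. Do not read a non-significant difference as equivalence.
- State the expected saline-day gap and set the margin below it. Otherwise RYGB without blockade would already count as equivalent to SG. A margin of ±74.5 kcal would therefore be inadmissible if the expected gap is 74.5 kcal or less.

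**(b) Restate the primary hypothesis** as the within-RYGB effect of blockade, or as the between-group difference in response. The plan already tests both.

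Route (b) costs only wording. Route (a) costs wording and one or two extra contrasts, and it makes equivalence harder to claim. Power falls further if both contrasts are required or the SD is larger, and may fall with covariate adjustment. If a justified margin is tighter than about ±72 kcal, route (a) would need more subjects and route (b) is the practical choice.

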is maintained in ~ 60% of patients at 5 years(10). This has led to a dramatic increase in the number of procedures performed annually from 13,365 in 1998 to an estimated 102,794 in 2003(11). A newer procedure, sleeve gastrectomy (SG) is a restrictive operation which has increased dramatically; comprising 34% of the ~ 110,000 bariatric surgeries performed in 2013 and may become the most frequent bariatric procedure in North America(12). SG may be cheaper than RYGB in terms of operative costs and because it is not a malabsorptive procedure, the costs of follow-up, and care of morbidities arising from malabsorption, should be lower(13). **Bariatric surgery effectively produces sustained weight loss in obesity and is widely performed in the United States**

2) Comparative effectiveness of RYGB and SG. It has been suggested that remission rate is associated with the length of bypass (~85% for standard RYGB, ~93% for long-limb RYGB and ~98% with duodenal switch(14; 15). Recent prospective, randomized controlled trials have however reported lower remission rates for diabetes with RYGB, although it remains superior to medical therapy(16-18). Kashyap et al. has suggested that differences in fat loss and β -cell function between RYGB and SG occur ≥ 1 year after surgery(19). Of the 2 studies with 3 year follow-up, one undertaken in nondiabetic subjects(20) did not demonstrate clear differences in weight loss while in the other (diabetic subjects) there were small, but significant, differences with RYGB superior to SG in terms of weight and glycemic control(21). However, there are obvious anatomic differences between procedures which result in differences in enteroendocrine secretion: postprandial GLP-1 concentrations are lower after SG compared to RYGB in the comparative studies undertaken in humans(19; 22-25). On the other hand, a liquid meal, especially after gastric restriction, may not recreate conditions present after a solid meal(26). Whether these differences can explain a divergence in metabolic outcomes remains unknown.

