Summary / Future Directions: There is evidence to suggest that post-prandial GLP-1 concentrations after RYGB influence satiety and caloric intake. This might be a mechanism by which RYGB has superior long-term effects on weight compared to SG. If this is indeed the case, GLP-1-based therapy could be utilized to maximize the benefit of surgical intervention after SG in subjects who are failing to lose weight or have suboptimal response to surgery. The combination of GLP-1 receptor agonist therapy and SG may provide equivalent or superior benefit to RYGB with less post-operative morbidity and mortality in the future. This application is intended to provide mechanistic data to support this notion prior to testing in a prospective, randomized controlled trial.

Analytic Techniques: All analytic techniques described in this and subsequent protocols are either established in the applicant's laboratory or are routinely performed in the Mayo GCRC Mass Spectrometry, Immunochemical Core laboratories of the Mayo CTSA. All blood will be immediately placed on ice, centrifuged at 4°C, separated and stored at -80°C until assay.

Glucose concentrations will be measured using an Analox glucose analyzer. C-peptide and glucagon concentrations will be measured using reagents purchased from Linco Research Inc., St. Louis, MO. Insulin will be measured using a chemiluminescence assay with reagents obtained from Beckman (Access Assay, Beckman, Chaska, MN). GLP-1 hormone concentrations will be measured: blood will be collected in ice-cooled EDTA-plasma tubes. Immediately after collection 100 μ M of a dipeptidyl peptidase-4 (DPP-4) inhibitor, Aprotinin (Linco Research, St. Charles, MO) will be added to the sample tube to prevent DPP-4 mediated degradation of intact GLP-1. All blood will be immediately placed on ice, centrifuged at 4°C, separated and stored at -80°C until assay. Hormone concentrations will be measured as previously described (61; 62). In addition, ghrelin, leptin and peptide YY (PYY) concentrations will also be measured by radio-immunoassay using reagents supplied by Linco Research (St. Louis, MO).

V. Human Subjects

Detailed Description: Suitable volunteers will be asked to visit the CRTU on a total of three occasions, including screening. During the first or screening visit they will meet with a member of the study team and

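### The primary claim that blockade brings RYGB intake up to the SG level presupposes a saline-day gap that no planned analysis estimates

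*Combined protocol and SAP*

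**What the plan says.** Section I states the primary hypothesis: "Blockade of the GLP-1 receptor in subjects after RYGB produces equivalent caloric intake to that observed after SG". Section IV, Interpretation, restates it as blockade that "increases caloric intake to amounts that do not differ from those consumed after SG in the presence or absence of Exendin-9,39 infusion". Both wordings have RYGB intake reaching the SG level, and the second says outright that it rises to get there. The lower starting point appears only as an expectation in the same paragraph: "We anticipate that after RYGB, subjects presented with a free choice buffet will eat less than subjects after SG during saline infusion". It comes with no size, no test and no condition.

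Section IV, Statistical Analysis, names two analyses. The first is within group: "The initial analyses will compare the within-group effect of treatment (Exendin-9,39) with the data observed in the study where saline is infused", and "This analysis will use a paired t-test, or signed-rank test, as warranted". The second is an ANCOVA that "will be used to test differences in the response to Exendin-9,39 between groups (RYGB vs. SG"), with the corresponding baseline study value, age, gender and weight as covariates. The power statement covers changes within each group only. Results are to be presented as observed means with SEM.

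**The concern.** The statement that blockade brings RYGB intake up to SG rests on two facts: RYGB intake is below SG intake on saline, and it no longer is under Exendin-9,39. The plan does not estimate the first. Without it, similar intakes under Exendin-9,39 do not show that GLP-1 explains a difference between the procedures, because there may have been no difference to explain.

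The gap cannot be taken for granted. Only infusion order is randomised. The groups are volunteers with existing surgery up to 10 years old. Section II, item 2, cites two studies with 3-year follow-up: the one in nondiabetic subjects "did not demonstrate clear differences in weight loss", and the one in diabetic subjects found small differences favouring RYGB. Both results concern weight rather than buffet intake, so they leave the question open without settling it either way.

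At stake is the between-procedure message in Summary / Future Directions: "This might be a mechanism by which RYGB has superior long-term effects on weight compared to SG".

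**Working it through.** **Inputs from section IV.** Caloric intake 745 Cal, SD 86; 25 per group; two-sided 0.05; 10% change = 74.5 Cal; about 85% power.

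**Assumptions, because the plan gives no figure.** Within-person correlation r between the two days of 0.04, 0.5 or 0.7; the same SD on both days; normal data; unadjusted tests.

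**1. The plan's own figure.** SD of the paired difference = SD × √(2(1 − r)). At r = 0.04 this is 86 × √1.92 = 119.2, with standard error 119.2/√25 = 23.8. The noncentrality is 74.5/23.8 = 3.13, and the paired t-test has 85% power. So the stated 85% is reproduced at r = 0.04, which is why that value is used. A two-sample t-test with the same inputs also gives 85.1%.

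**2. What each planned analysis estimates.**
- Paired test in RYGB: RYGB on Exendin-9,39 minus RYGB on saline.
- Paired test in SG: SG on Exendin-9,39 minus SG on saline.
- ANCOVA: the between-group difference in response, given the baseline study value. Buffet intake exists only from 240 min on each study day, so the natural reading of that covariate is the saline-day intake. It is then adjusted for, not compared.

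None of the three estimates RYGB minus SG on saline.

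**3. How often the conclusion is supported with no gap.** Simulation with 60,000 trials per setting, SD 86 and equal true saline means. The criterion follows the Interpretation wording. RYGB rises significantly, and RYGB on Exendin-9,39 does not differ significantly from SG on Exendin-9,39 or from SG on saline.

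| True effect of Exendin-9,39 | r = 0.04 | r = 0.5 | r = 0.7 |
|---|---|---|---|
| None in either group | 2% | 2% | 2% |
| 5% (37.25 Cal) in RYGB only | 9% | 26% | about 43% |
| 10% (74.5 Cal) in both groups | 9% | 12% | 13% |
| Same, and SG change must be non-significant | 4% | 0.6% | 0% |

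The second row is the one the planned tests do not screen out. With 25 per group, a two-sample test has 32% power for a 37.25 Cal difference. About 68% of trials therefore find no significant RYGB–SG difference under Exendin-9,39, although RYGB now truly exceeds SG. Also requiring a non-significant SG change barely alters that row (9%, 25%, 41%). A significant ANCOVA would be read as the larger RYGB response that the plan expects.

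**4. What the missing estimate could show.** Standard error of a two-group difference = 86 × √(2/25) = 24.3 Cal. The 95% CI half-width is 2.011 × 24.3 = 48.9 Cal. Power to show a 74.5 Cal saline gap is 85% at SD 86, 58% at an assumed SD of 120 and 41% at an assumed SD of 150.

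**The case against.** A reader might infer that the plan is nearly certain to mislead. Suppose there is no gap and both groups rise by 10%. RYGB then rises significantly and does not differ significantly from SG under Exendin-9,39 in 81%, 94% and 95% of trials (r = 0.04, 0.5, 0.7). The documents do not support that as the size of the problem. The plan also tests the change within SG and says it expects little or none. Requiring a non-significant SG change cuts those rates to about 12%, 1% and 0%. The Interpretation wording also refers to SG intake with and without Exendin-9,39, which by itself brings the rates to 9–13%. These reductions weaken if intake varies more. At an assumed SD of 150, the equal-rise case passes both SG comparisons in 16%, 34% and 48% of trials, and in 13%, 15% and 8% if the SG change must also be non-significant.

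Three further replies deserve weight. If Exendin-9,39 does nothing, the required RYGB increase holds the error near 2%. That is correct, but the plan expects an increase. The observed means with SEM would show an absent gap. That is also correct, but no rule links them to the conclusion. Finally, the inference that endogenous GLP-1 reduces intake after RYGB rests on a within-person comparison in random order and needs no gap. That stands in full; only the between-procedure claim is affected.

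**Conclusion.** The concern holds in a limited form. The comparison that the primary claim presupposes is not among the planned analyses, and the plan can be followed exactly and still support that claim where no saline-day gap exists. With a 5% rise in RYGB only, this happens in about 9% to 43% of trials as r goes from 0.04 to 0.7. With an equal 10% rise it happens in 9–13%, or 4% or less if the SG change must also be non-significant.

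These figures rest on the plan's SD of 86, the assumed correlations and the criterion in step 3. The plan itself names no test for its wording that intakes do not differ. The SD comes from a cited study whose title places it in type 2 diabetes, whereas this trial excludes subjects with diabetes after surgery, so a different buffet SD is quite possible.

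The documents do not show that the conclusion would be false, that the gap is absent, or that the planned paired tests and ANCOVA are wrong for the questions they answer. This is a cheap improvement to the plan, not a fault that invalidates it.

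**What to change.** Add to Statistical Analysis:

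> Saline-day buffet calories will be compared between RYGB and SG (mean difference with 95% CI, with and without adjustment for age, gender and weight). The result will be reported beside the same difference on the Exendin-9,39 day and the between-group difference in response. A statement that blockade brings RYGB intake up to SG, or that GLP-1 explains a difference between procedures, will be made only to the extent that the saline-day estimate and its CI support a lower RYGB intake. Otherwise the result will be reported as a within-RYGB effect of Exendin-9,39.

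It should also say explicitly that the ANCOVA's baseline study value is the saline-day intake for this outcome, if that is what is meant.

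The cost is one more comparison of data already collected and perhaps a more cautious conclusion, since the CI is about ±49 Cal at SD 86 and wider if intake varies more. A rule requiring a statistically significant saline gap is not recommended. Take a true 74.5 Cal gap that blockade fully closes, and count the claim as made when RYGB rises significantly and does not differ significantly from SG under Exendin-9,39. At an assumed SD of 150, the gate would cut correct claims from 38%, 63% and 83% to about 23%, 30% and 36% (r = 0.04, 0.5, 0.7).
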